#### 7.1.3.1.3.2 Immune Profiling of T cell Repertoire

The studies proposed will evaluate the T cell receptor (TCR) diversity in T cells isolated from PB and BM from AML patients before and after treatment with AZA/pembrolizumab on the parent clinical trial. We will determine TCR diversity and clonal composition using a molecular and computational approach based on high-throughput DNA sequencing of rearranged TCR $\beta$  CDR3 regions from T cell genomic DNA. This approach allows direct measurement of the TCR $\beta$  CDR3 region sequence diversity in any arbitrarily complex population of T cells, and also permits quantitative description of the clonal composition of the population. The [name] laboratory in collaboration with the [name] laboratory from Fred Hutchinson Cancer Research Center (FHCRC) is routinely performing this comprehensive in-depth analysis of the TCR repertoire in patients with MDS/AML treated with ipilimumab and have performed extensive monitoring and tracking of the TCR repertoires in patients undergoing allo-SCT (manuscript in preparation). We are utilizing an established multiplex PCR strategy to amplify the CDR3 region of the TCR, spanning the variable region formed by the junction of the V, D and J segments and their associated non-template insertions followed by Illumina-based sequencing methodology, a well-characterized methodology developed by Adaptive Technology (<http://www.adaptivebiotech.com/technology/>). Sequencing is followed by comprehensive bioinformatics analyses focused on determining the diversity of the T cell and B cell repertoires as well as the entropy and clonality of each repertoire consistent with previous studies. Through these ongoing studies we have developed substantial experience not only in using and analyzing DNA retrieved from unsorted PBMCs but also from sorted T cells subpopulations (naïve vs memory vs regulatory), paired PB and BM samples and as well from DNA retrieved from FFPE archived tissues. We hypothesize that a primary action of AZA/pembrolizumab will be to disrupt the skewed T cell pattern present in AML patients prior to treatment toward increased TCR diversity and the emergence of unique TCR clonotypes that may be relevant in the anti-leukemia response. The long-term goal of this work is to uncover antigen- specific responses that, together with the other proposed correlative studies, will provide deeper insight into the mechanisms involved in anti-leukemic immune responses after AZA/pembrolizumab treatment.

#### 7.1.3.1.3.3 T cell Methylation Analysis

We will examine IL-2 and PD-1 promoter methylation status in T cell subsets to gain insight into the changes in DNA methylation and expression of IL-2 and PD-1 before and after treatment. We will perform bisulfite sequencing to assess the level of DNA methylation at the individual CpG sites of the IL-2 and PD-1 promoter in T cells. Both CD4+ and CD8+ T cells from PB and BM will be analyzed. CD4+ and CD8+ T cells will be isolated by either magnetic cell separation or by flow cytometric sorting. Sequencing of at least 10 individual clones from

each sample will be performed. All independent experiments will be duplicated to avoid any PCR amplification bias. These studies will be coupled with those measuring mRNA production of IL-2, PD-1 and other effector cytokines. The overarching goal of these studies is to determine the relationship between IL-2 and PD-1 promoter DNA methylation and T cell differentiation status and its relation to the response to AZA/pembrolizumab treatment.

#### 7.1.3.1.3.4 Assessment of serum pro-inflammatory and inhibitory cytokines

We will investigate changes in the cytokine levels in patients before and after treatment with azacitidine/pembrolizumab. We predict that levels of pro-inflammatory cytokines (IL-12, IFN- $\gamma$ , RANTES) will be higher while those of inhibitory ones (IL-10, TGF- $\beta$ ) will be lower in patients treated with azacitidine/pembrolizumab.

#### 7.1.3.1.3.5 DNA Sequencing and Gene expression profiling

Bone marrow aspirates will be used to perform RNA sequencing, or to examine mRNA gene expression by gene array technology and/or quantitative real-time polymerase chain reaction (qPCR) to detect expression of selected immune related genes before and after treatment. In addition, whole or targeted exome sequencing on the leukemia cells may be performed (lymphocyte control) for detection of immunogenic neoepitopes.

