## PD-1 Post-alloHSCT

In clinically relevant murine models of alloHSCT, the recipient antigen expression by non-hematopoietic cells promotes T cell exhaustion and abrogates the graft vs leukemia (GVL) reactivity through upregulation of PD-1 on donor T cells. Donor T cell dysfunction could partially be restored by blockade of PD-L1 and delayed blockade of PD-L1 after transplant improved the beneficial GVL effect without inducing graft vs host disease (GVHD). In patients relapsing after alloHSCT, PD-L1 was found to be upregulated on leukemic progenitors. Furthermore, high PD-1 expression was noted on allo-reactive minor histocompatibility antigen (MiHA)-specific effector memory CD8+ T cells (TEMs). *Ex vivo* treatment with monoclonal antibodies (mAbs) against PD-1 or PD-L1 restored the proliferation and IFN- $\gamma$  production of MiHA-specific TEMs, more potently in relapsed patients than in those in remission. Similarly, silencing of PD-L1 and PD-L2 on MiHA-loaded dendritic cells augmented the expansion of functional MiHA-specific TEMs from leukemia patients early after DLI and later during relapse. Safety of immune checkpoint blockade after alloHSCT has been demonstrated for ipilimumab, a mAb targeting CTLA-4. Thus, it is reasonable to hypothesize that PD-1 blockade will be feasible, may bolster donor specific T cell responses,

and consequently augment a GVL effect in patients who relapse post-alloHSCT as long as it is administered to patients having no evidence of active GVHD and not requiring ongoing immune suppression.

All together, these data suggest that epigenetic therapy with azacitidine combined with blockade of PD-1/PD-L1 pathway is a rational therapeutic approach both in newly diagnosed older patients and those with relapsed and refractory AML. Furthermore, recent data suggest that the addition of PD-1 blockade (nivolumab) to azacitidine in patients with AML who have previously failed hypomethylating agents may induce responses in up to 20% patients (Daver N; ASH abstract #763, ASH 2016), which is comparable to the responses obtained with intensive salvage therapies (for which many of AML patients may not be eligible due to age and co-morbidities).

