## 5.0 METHODOLOGY

### 5.1 Entry Criteria

#### 5.1.1 Diagnosis/Condition for Entry into the Trial

1. Relapsed and refractory acute myeloid leukemia (**Cohort 1**) – This cohort has enrolled the expected 40 patients and is now completed.
2. Newly diagnosed acute myeloid leukemia in older patients ( $\geq 65$  years) not candidates for intensive induction chemotherapy (**Cohort 2**) – This cohort is closed to new accrual as of 1/8/2020 based on risk benefit analysis information received from the FDA on 1/3/2020.

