##### Cohort #1

1. Have histologically or cytologically confirmed relapsed or refractory AML (i.e.  $\geq 5\%$  blasts by manual differential on bone marrow aspirate/biopsy/flow cytometry), excluding acute promyelocytic leukemia (APL; FAB M3; t(15;17)).
2. Be willing and able to provide written informed consent/assent for the trial.
3. Be  $\geq 18$  years of age on day of signing informed consent.
4. Not be appropriate candidate for intensive salvage chemotherapy due to co-morbidities or other disease- or treatment-related factors.

NOTE: Subjects who received prior treatment with hypomethylating agents either for Myelodysplastic Syndrome (MDS), Myeloproliferative Neoplasm (MPN), or AML will be eligible.

NOTE: Subjects who had prior allogeneic stem cell transplant (alloHSCT) will be eligible as long as they have been at least 3 months after allogeneic HSCT and are off of all immune suppression for at least 3 weeks ( $>21$  days) and have no evidence of active graft versus

host disease (GVHD). Subjects with prior alloHSCT will NOT be eligible for enrollment during the safety run in phase.

5. Demonstrate adequate organ function as defined in Table 1, all screening labs should be performed within 14 days of treatment initiation.
6. ECOG performance status < 2.
7. A projected life expectancy of at least 12 weeks.
8. Female subject of childbearing potential should have a negative urine or serum pregnancy within 72 hours prior to receiving the first dose of study medication. If the urine test is positive or cannot be confirmed as negative, a serum pregnancy test will be required.
9. Female subjects of childbearing potential (Section 5.8.2) must be willing to use an adequate method of contraception as outlined in Section 5.8.2 – Contraception, for the course of the study through 120 days after the last dose of study medication.

Note: Abstinence is acceptable if this is the usual lifestyle and preferred contraception for the subject.

10. Male subjects of childbearing potential (Section 5.8.2) must agree to use an adequate method of contraception as outlined in Section 5.8.2- Contraception, starting with the first dose of study therapy through 120 days after the last dose of study therapy.

Note: Abstinence is acceptable if this is the usual lifestyle and preferred contraception for the subject.

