### **8.2 Statistical Analysis Plan**

#### **8.2.1 Safety Run-In**

Each cohort will be enrolled separately with distinct null hypotheses and statistical plans. Since azacitidine and pembrolizumab have not been tested previously in combination in AML patients, we plan first to start enrollment with Cohort 1 (a safety run-in phase). Recognizing that Cohort 1 may also include patients who relapsed after allogeneic hematopoietic stem cell transplant (alloHSCT) and thus may have differential sensitivity (tolerability, immune-related adverse events [IRAEs]) to this drug combination, we will start enrollment in Cohort 1 to include patients who did not have prior alloHSCT.

The primary objective of the safety run-in is to determine the safety and tolerability of AZA followed by pembrolizumab in relapsed and refractory AML using a 3+3 design. We plan to monitor for DLTs in cycles 1, 2 and 3 as some of immunological side effects associated with pembrolizumab may occur with the delay. The first three patients will be enrolled and receive planned azacitidine and pembrolizumab in cycle 1. If 0 or 1 patient of the first three patients has a DLT (dose limiting toxicity) in cycle 1, we will enroll an additional 3 patients to better assess for toxicities. If less than 2 among first 6 patients experiences DLT in the cycle 1-3, we will open enrollment in Cohort 1 for all relapsed/refractory patients including those with prior history of alloHSCT and will also start to enroll patients in Cohort 2. If  $\geq 2$  of the first 3 patients or  $\geq 2$  of 6 patients have DLTs during cycle 1, we will perform safety (detailed toxicity) review to assess for disease versus treatment-related toxicities. Given that pembrolizumab is given only once in cycle 1 (day 8), we will first dose de-escalate azacitidine as detailed in Section 2.2. However, if the safety data analysis suggests that the toxicities are more likely pembrolizumab related, an alternative approach we may take is to exclude pembrolizumab in cycle 1 and start pembrolizumab dosing in cycle 2 when AML is better controlled but maintain azacitidine dose/schedule as described in Section 2.2. If

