## 11.4 Operating Procedures for Specimen Collection

Peripheral blood and bone marrow specimen collection will be performed as delineated in the Trial Flow Chart Section 6.0. and at the times when peripheral blood and bone marrow collections are performed for clinical care. Please see details in the Laboratory Manual.

**Bone marrow:** 5x8.5mL will be collected in light yellow top ACD tubes (or 4x10mL green top heparin tubes) (~40 mL) . Re-adjustment of the direction of bone marrow aspirate needle should take a place after each 10 cc is collected to prevent hemodilution. At the time of collection, green top tubes must be thoroughly mixed to prevent clotting.

**Peripheral blood:** 5x8.5mL light yellow top ACD tubes (or 4x10mL green top heparin tubes) of blood (~40mLs) will be collected at each time point.

Specimens should be labeled with the patient's study number (given at the time of registration), study number, sample collection date and time, and sample source (PB or BM). Sample collection date and time, and sample source (PB or BM) will be recorded on correlative collection worksheet and copy included with delivery. All data should be kept in laboratory log. At each sampling time, BM and PB mononuclear cells (PBMC) will be processed via Ficoll density gradient centrifugation. The washed cells will be counted, triaged for DNA isolation, and viably cryopreserved using a controlled-rate freezer with transfer to the vapor phase of liquid nitrogen for long-term storage.

The Sidney Kimmel Comprehensive Cancer Center (SKCCC) specimens should be delivered to the [name] laboratory immediately after collection.

Specimen collection / processing (Participating Sites). Participating sites should collect PB and BM specimens as outlined in the Trial Flow Chart 6.0. Participating sites have two options:

1) To process specimens following the SOP described below. Samples will be stored at each study site. Any samples collected under the clinical protocol will be batch

shipped on dry ice based on discussions with the participating site PI, Study Chair and [name].

[figure not shown]
2) If participating site does not have capability of processing the specimens as described below, then specimens can be shipped overnight to [name] laboratory using cold shipping packages (boxes) provided by Fedex. Please notify PI (Study Chair), study coordinator and [name] laboratory of specimen shipment.

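### The lymphocyte control named for neoepitope exome sequencing does not supply the patient's inherited genome in Cohort 1 patients with a prior allograft

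*Combined protocol and SAP*

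**What the plan says.** Section 7.1.3.1.3.5 describes optional sequencing: "whole or targeted exome sequencing on the leukemia cells may be performed (lymphocyte control) for detection of immunogenic neoepitopes". The parenthesis is the only statement in the documents about the normal comparator. Section 4.2.3.2 also lists exome sequencing as something that may be done.

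Section 5.1.2, Cohort #1, criterion 4 opens the cohort to allograft recipients: "Subjects who had prior allogeneic stem cell transplant (alloHSCT) will be eligible", subject to time since transplant, being off immune suppression and having no active GVHD. There is one restriction: "Subjects with prior alloHSCT will NOT be eligible for enrollment during the safety run in phase". Section 8.2.1 acknowledges these patients in Cohort 1, and section 8.2.2.2 gives patients with prior alloHSCT their own GVHD stopping rule, so they are an expected subgroup.

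On specimens, Appendix 11.4 says: "Peripheral blood and bone marrow specimen collection will be performed as delineated in the Trial Flow Chart Section 6.0". The Trial Flow Chart footnotes and section 7.1.5.1.1 likewise mention only blood and marrow.

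**The concern.** A normal control in tumor sequencing must carry the patient's inherited genome, so that subtracting it leaves only acquired changes. A donor-engrafted patient's lymphocytes carry the donor's genome. If the leukemia is the recipient's, the comparison mixes two people: inherited recipient alleles absent from the donor survive the subtraction and look acquired.

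The interpretation of the neoepitope list is at stake. Section 4.2.1 itself discusses T cells specific for minor histocompatibility antigens in patients relapsing after alloHSCT. Those antigens come from inherited donor-recipient differences. Listing them as neoepitopes would merge an alloreactive target with a tumor-specific one, in the subgroup where the distinction matters most. Section 4.2.3.2 makes finding candidate predictive biomarkers a goal of the correlative program, so a list built this way could later be put to that use.

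**Working it through.** The plan gives no figure on this point to reproduce. The check sets the passages side by side, bounds the number of patients, and gives one labelled illustration.

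**1. Does the control fit every patient it could be applied to?**

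- Control: lymphocytes, with no exception by transplant history (section 7.1.3.1.3.5).
- Patients: Cohort 1 includes allograft recipients after the run-in (sections 2.1, 5.1.2 and 8.2.1). The eligibility text mentions prior alloHSCT only for Cohort 1; Cohort 2 takes newly diagnosed AML not previously treated.
- Origin of the lymphocytes: the rationale in section 4.2.1 expects PD-1 blockade to strengthen donor-specific T cell responses in patients who relapse after alloHSCT. The same section describes a mechanism that "abrogates the graft vs leukemia (GVL) reactivity through upregulation of PD-1 on donor T cells". That sentence concerns mouse models, so the expectation about patients carries the weight.
- Origin of the leukemia: taken as the recipient's, the usual case and the one that a graft-versus-leukemia rationale presupposes.
- Another source of inherited DNA: none appears. The documents mention no non-hematopoietic sample, stored pre-transplant DNA, donor sample, chimerism test or population-variant filter, and section 8.2.5 has no rule for allograft recipients in sequencing work.

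Followed as written, the stated control gives a wrong result in this subgroup.

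**2. How many patients could be affected?**

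- Enrolled in Cohort 1: 40. Section 5.1.1 says "This cohort has enrolled the expected 40 patients and is now completed".
- Planned run-in: 6 (Table 3, section 5.2.1.3), none with prior alloHSCT.
- Ceiling: 40 − 6 = 34, or 34/40 = 85%. Floor: 0, because no count of allograft recipients is given.
- The ceiling treats the six as part of the 40. Section 8.2.1 allows at most two de-escalations with 6 more patients each. If all of those also counted among the 40, the ceiling would be 40 − 12 = 28 or 40 − 18 = 22.

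**3. Illustration of the direction and the chance per site (assumptions, not trial data)**

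Assume Hardy-Weinberg proportions, full donor chimerism and leukemia that keeps the recipient's inherited alleles. For a variant of frequency p, with q = 1 − p, a false somatic call needs the recipient to carry the variant and the donor to lack it:

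- unrelated donor: q²(1 − q²)
- parent or child donor: q² − q³
- sibling donor: q² − (q²/4 + q³/2 + q⁴/4)

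| p | Unrelated | Parent/child | Sibling |
|---|---|---|---|
| 0.01 | 2.0% | 1.0% | 1.0% |
| 0.05 | 8.8% | 4.5% | 4.5% |
| 0.1 | 15.4% | 8.1% | 7.9% |
| 0.2 | 23.0% | 12.8% | 12.2% |
| 0.3 | 25.0% | 14.7% | 13.6% |
| 0.5 | 18.8% | 12.5% | 10.9% |

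For example, at p = 0.3 with an unrelated donor: 0.49 × 0.51 = 0.2499. With a control carrying the patient's own inherited genome, the chance is 0% throughout. These are chances per site. A count of false calls would also need the number of sites sequenced and their allele frequencies, which the documents do not give.

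**The case against.** The strongest reply is that this concerns a two-word parenthesis about an optional assay. The plan does not say which patients would be sequenced or how variants would be called. Appendix 11.4 refers to a Laboratory Manual that was not available for this review and might name another control. Population-variant filtering would remove many common inherited variants, and mixed chimerism would leave some recipient alleles in the control.

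Much of this stands as a limit on size. The assay is exploratory, the error can be partial, and the Laboratory Manual cannot be ruled out. It does not remove the point: the one control that is named is unsuitable for a subgroup the protocol deliberately admits, and no safeguard is mentioned.

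Four stronger readings are tempting and are not supported:

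- A reader might infer that nearly all candidate neoepitopes in these patients would be false. That needs counts of true mutations and of donor-recipient differences, which the documents do not give. Targeted sequencing, which is also allowed, would change both.
- A reader might infer that every donor-recipient difference would be miscalled. Alleles that only the donor carries would not be reported as leukemia mutations.
- A reader might infer that a planned neoepitope-response analysis is confounded by transplant history. Section 8.2.5 specifies no such analysis and does not mention exome data; section 7.1.3.1.3.5 speaks only of detection.
- A reader might take 34 of 40 as an estimate. It is a ceiling.

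**Conclusion.** The concern holds as a minor point. In Cohort 1 patients with a prior allograft, the stated lymphocyte control would cause inherited coding variants that the recipient has and the donor lacks to be listed as leukemia mutations and candidate neoepitopes. These may be immunogenic as minor histocompatibility antigens, so the error is one of labelling: they are not somatic.

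The size is bounded only loosely: 0 to at most 34 of 40 Cohort 1 patients, and an unknown number of false calls in each. The conclusion assumes that the sequencing is done, that lymphocytes sampled on study serve as the control, that they are wholly or largely donor cells, and that the relapsed leukemia is the recipient's. In a donor-derived leukemia the pattern would differ. The primary and secondary endpoints, sample size, monitoring rules and safety are untouched.

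**What to change.** In section 7.1.3.1.3.5, limit the lymphocyte control to patients without prior alloHSCT. For allograft recipients, use stored pre-transplant recipient DNA where it already exists; otherwise exclude them from somatic neoepitope calling. Add to section 8.2.5 that any neoepitope result is reported separately by prior alloHSCT. If the Laboratory Manual already names another control for these patients, section 7.1.3.1.3.5 should say so.

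Closed enrollment is no obstacle. Prior cancer treatments are reviewed under section 7.1.1.5.2, so transplant history should be known, and processed cells are cryopreserved under Appendix 11.4. The change is a few sentences and needs no new study sample. The cost is fewer patients in the exploratory neoepitope analysis, possibly many fewer in Cohort 1 if allograft recipients are common and pre-transplant DNA is scarce. A non-hematopoietic sample could keep them in, but it is not among the specimens collected and would go beyond a wording change.

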#### 7.1.3.1.3.6 Characterization of tumor-infiltrating lymphocytes (TILs) and tumor antigens

Immunohistochemistry (IHC) will be used to assess the number and composition of immune infiltrates in order to define the immune cell subsets present within bone marrow before and after exposure to azacitidine and pembrolizumab. These IHC analyses will include, but not necessarily be limited to, the following markers: CD4, CD8, FOXP3, PD-L1, and PD-L2. Correlations between gene expression and IHC expression will be made between assays performed if deemed to be informative.

### 7.1.4 Other Procedures

#### 7.1.4.1 Withdrawal/Discontinuation

When a subject discontinues/withdraws prior to trial completion, all applicable activities scheduled for the final trial visit should be performed at the time of discontinuation. Any adverse events which are present at the time of discontinuation/withdrawal should be followed in accordance with the safety requirements outlined in Section 7.2 - Assessing and Recording Adverse Events. Subjects who a) attain a CR as specified in Section 5.9.1 or b) complete 24 months of treatment with azacitidine and pembrolizumab may discontinue treatment with the option of restarting treatment if they meet the criteria specified in Section 7.1.5.5. After discontinuing treatment following assessment of CR, these subjects should return to the site for a Safety Follow-up Visit (described in Section 7.1.5.3.1) and then proceed to the Follow-Up Period of the study (described in Section 7.1.5.4).

